Appendix 7: Study Two Phone Survey 2 (4-weeks post vaccine)

PIPS Patient Participant Phone Survey (4 weeks post vaccine)

Researcher: _____ **Date:** _____

The following questions ask about your memory of events for the period up to 4 weeks following when you received the Tdap vaccine (whooping cough vaccine).

	Yes	No	Date started	Date resolved/ recovered	Resolving/ recovering	Not resolved/ recovered	Resolved/ recovered with lasting effects
1. Have you experienced any adverse events/symptoms within the one month post vaccination?							
2. Since receiving the vaccine, have you had any infections such as a: urine, ear, nose, throat, lung infection, gastroenteritis, skin infections							
3. Since receiving the vaccine, have you experienced any of the following:							
Muscle aches and pains							
New onset high blood pressure							
Severe nausea or vomiting							

Pertussis in Pregnancy Safety (PIPS) Study Protocol
 Confidential
 Not for Public Circulation or Reproduction

Premature labour							
Premature rupture of membranes							
Severe abdominal pain							
Vaginal bleeding							
Depression or psychological disorders							
Unexplained itching of the skin							
Spontaneous abortion or threatened abortion							
4. Since receiving the vaccine, have you needed to see a doctor for any of the events described above or for any other reason?		If no, go to end.	If yes, please indicate where you saw the doctor:  Emergency Room/After Hours  Hospital  GP Practice				
4b. What was the diagnosis?							
4c. If there was no diagnosis, what were the signs and symptoms?							

4d. Can we contact your family doctor for further details?
(If yes, please provide Dr name and hospital/practice details)

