Rates and patterns of adverse events in women who were administered Tdap during pregnancy

Multiple pregnancies

While the number of visits during pregnancy could have an impact on the pregnancy outcome within the study population in Study Two and Three (but not in Study One). The frequency of prenatal care is a potential confounder as it may be associated both with women receiving Tdap or not, and with birth outcomes. There is no way to capture the number of prenatal visits women have from nationally available data. However, the National Maternity Collection does “contain data on primary maternity services provided under Section 88 of the NZ Public Health and Disability Act 2000. This information is sourced from lead maternity carer claims for payment.” This information might be useable as a proxy to indicate frequency of prenatal care.

Study Three: Intensive monitoring study of pregnant women administered Tdap during pregnancy and their infants

Study Three involves extending and supporting the intensive monitoring study currently being conducted in the Canterbury DHB by [name] (Principal Investigator). Briefly this study runs as per Study Two except the women and their infants are followed up intensively for a period of one year after the birth of the infant. The data collected for the period of one month post vaccination in Study Three will be able to be pooled for the overlapping subset of participants also in Study Two.

Study Three includes women receiving the vaccine under the DHB programme at 30–36 weeks in the Canterbury region.

Figure 1. Study population and outcomes

[figure not shown]
[figure not shown]

Figure 2. Monitoring of pregnant women receiving pertussis during pregnancy

Canterbury DHB continues intensive follow up for birth outcomes and infant outcomes for one year for a sample of 300 women and their infants. Infant follow up at three to seven months and 12 months of age in this DHB as per Canterbury protocol (Study Three) (Appendix 8).

Study procedures

Study One (utilising whole population data-linking)

Data sets for hospitalisations, pertussis notifications, infant vaccination and maternal Tdap vaccination will be obtained for the period 1 January 2009 to year ending 2013 from the following national databases:

- National Minimum Dataset for hospitalisation data
- The National Immunisation Register for infant immunisation data
- Notification data from the ESR
- Pregnancy Immunisation records from the HealthPAC claims database

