- Estimated minimum and maximum number of women for follow up of pertussis vaccine 1,527–20,358

Sample size and power

As this is an observational study we plan to describe the confidence intervals for the proportions of AEs. With a sample of 300 vaccinated participants, if event occurs in 10% of the group the 95% CI would be 7–14%; if 5%, 2.8–8.1%; if 1%, 0.2–2.9%. Additional power will be achieved by combining the data from the Canterbury study (Study Three), which aims to include 300 women vaccinated with Tdap.

Statistical Analyses

The pregnancy safety data will be descriptive in nature, including percentages and 95% confidence intervals. The rates of AEs and SAEs following pertussis vaccine will be discussed in context with the rates previously described for pertussis. The expected background rates of MAEs and SAEs for Tdap given during pregnancy are unknown, but as a guide the rates of MAEs for pregnant women receiving influenza vaccine previously reported ranged from 1.1 to 3.8% while the rate of SAEs ranged from 0.4 to 1.5%.

Women who have complicated pregnancies will be excluded from the final analyses and described separately.

The temporal relationship between onset of events and vaccination will be presented including distribution where appropriate.

Serious adverse events will be reported as detailed clinical cases. Other events will be groups according to Brighton Collaboration Definitions.

Study Three (N=~300)

From the protocol for Canterbury DHB (Appendix 8): Principal Investigator, [name].

As this study is an observational study, the pregnancy outcomes and safety data will be descriptive in nature. The rates of AEs and SAEs will be compared to published background rates for the general population. The expected rates of MAEs and SAEs for Tdap given during pregnancy is unknown, but as a guide the rates of MAEs for pregnant women receiving influenza vaccine in this paper ranged from 1.1 to 3.8% while the rate of SAEs ranged from 0.4 to 1.5%. Where the known background incidence of 0.01 for a particular adverse event, a sample size of 300 achieves 80% power to detect an additional incidence rate of 0.0175 when the significance level is 0.05.

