
Level one diagnostic certainty is: Any description of morphological or physiological change at or near the injection site that is described or identified by a health care provider
 
Level two diagnostic certainty is: Any description of morphological or physiological change at or near the injection site that is described or identified by another person
	
Fever Endogenous elevation of at least one measured body temperature of $\geq 38^{\circ}\text{C}$
 
 • Time intervals 
 ○ 0 – 24hr Day 1 ○ 0 – 24hr Day 2 ○ Day 3-7... • Increments

Categories for event classification
 
 • Level 1: as specified in the case definition for a local reaction • Level 2: as specified in the case definition for local reaction 
Insufficient evidence for a local reaction
 
Not a case of a local reaction
 
Interval for onset of local reaction or first observation
 
 • >0-24 h • 25-48 h • 49-72h • 73h – 7 days • >7 days • Include numbers of subjects with local reactions newly present at each specified time as %. 
Diameter of the local reaction
 
 • >0.0 - <1.0 cm • ≥1.0 – 2.5 cm • ≥2.5 – 5.0 cm • ≥5.0 - <10.0 cm • ≥10.0 - <15.0 cm • ≥15.0 - <20.0cm • ≥20.0 - <30.0 cm • ≥30.0 cm 
Pain scale to include measure of functionality
 
 • 0 = No pain • 1 = Mild, still able to move arm normally • 2 = Moderate, hurts to move arm normally or to touch • 3 = Severe, unable to move arm 	
 ○ <38°C ○ 38.0-38.4°C ○ 38.5-38.9°C ○ Etc.... >41°C
--	--

Pertussis in Pregnancy Safety (PIPS) Study Protocol
Confidential
Not for Public Circulation or Reproduction

Appendix 5: Written questionnaire (medically attended adverse events in mother in first 4 weeks after vaccine)

Period _____ **to** _____

	Yes	No	Date started	Date Resolved	Resolving	Not Resolved	Resolved with lasting effects
Have you experienced any adverse events within the one month post vaccination?							
Any infections							
For example: urine infections, ear, nose, throat or lung infections, gastroenteritis, and skin infections. Circle which one.							
Muscle aches and pains							
New onset high blood pressure							
Severe nausea or vomiting							

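### The Study Two four-week survey has no field to name an adverse event that is unlisted, not seen by a doctor and not already named at the first call

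*Protocol*

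**What the plan says.** The Study Two design section undertakes to describe any adverse event in vaccinated mothers within one month of immunisation. The endpoint is "Rates and patterns of adverse events in women who were administered Tdap during pregnancy", and the Study Two analysis text adds "Other events will be groups according to Brighton Collaboration Definitions".

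Two phone interviews supply the data. The second, at four weeks (Appendix 7), has this structure:

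- Item 1: "1. Have you experienced any adverse events/symptoms within the one month post vaccination", with columns for Yes, No, two dates and three resolution statuses.
- Item 2: "2. Since receiving the vaccine, have you had any infections such as a: urine, ear, nose, throat, lung infection, gastroenteritis, skin infections", in one row.
- Item 3: "3. Since receiving the vaccine, have you experienced any of the following", followed by ten named conditions.
- Item 4: "4. Since receiving the vaccine, have you needed to see a doctor for any of the events described above or for any other reason". A No ends the interview; a Yes leads to diagnosis (4b), or signs and symptoms if there was no diagnosis (4c).

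The Canterbury four-week questionnaire (Appendix 5 within Appendix 8) opens with "Have you experienced any adverse events within the one month post vaccination" and has a similar list. At the infection row it tells the woman "Circle which one".

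**The concern.** Item 1 is an open question, so it invites events outside the lists in items 2 and 3. The form then has nowhere to write down what the event was unless a doctor was seen. The record holds a Yes, perhaps a date and a status, and no term.

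The overall proportion of women reporting any event can still be computed. The pattern by type cannot be completed for these events, and no later analysis can recover a term that was not recorded. If several such events occur in one woman, a single row of dates and status has to stand for all of them. In item 2, seven kinds of infection share one Yes/No, so an infection managed without a doctor has no type.

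**Working it through.** The point turns on no calculation. The only figures tied to this endpoint are the 95% intervals for 300 women under Sample size and power. They reproduce by the exact (Clopper-Pearson) method: 30/300 gives 6.8–14.0% (stated 7–14%), 15/300 gives 2.8–8.1%, and 3/300 gives 0.2–2.9%. Those intervals are not in question.

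The check is to trace each kind of event through the forms as written and ask where its name is recorded.

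1. **On the item 3 list, doctor or not:** named by its row.
2. **Unlisted, doctor seen:** item 1 Yes, item 4 Yes, named at 4b or 4c.
3. **Unlisted, no doctor, present at the first call:** named in Survey 1 (Appendix 6), whose question on other symptoms ends with an 'Other' row asking for details.
4. **Unlisted, no doctor, first arising or first reported after that call:** item 1 Yes, item 2 No, item 3 all No, item 4 No, end. Fields holding an event name: 0.
5. **Infection, doctor seen:** type available at 4b.
6. **Infection, no doctor:** item 2 Yes, item 4 No, end. Fields holding the type: 0.
7. **Two or more events of kind 4 in one woman:** one row, hence one onset date, one resolution date and one status.

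The gap is rows 4, 6 and 7.

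**How much of the month is exposed.** Survey 1 is scheduled at 48 hours to 7 days. If the call is made on schedule, the four-week form alone covers the remaining 28 − 7 = 21 to 28 − 2 = 26 days. A first call made late would shorten that period but rely more on recall.

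**Other routes to a name.** Under Study procedures, the practice verifies only events that needed a consultation, which excludes rows 4 and 6. The data management section says the database receives what is reported on the survey forms. An interviewer's marginal note therefore has no planned destination.

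**Counting the gap afterwards.** A Yes at item 1 with No everywhere else is identifiable as an unnamed event. A Yes at item 1 together with a Yes in item 2 or 3 is ambiguous: item 1 may refer to the listed event or to a further one. The form therefore gives only a lower bound on the number of women with an unnamed event.

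**The case against.** Much can be said for the form, and most of it limits the point.

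- **The first days are covered.** Survey 1 and the Canterbury first-contact questions both have an 'Other' row with details. A reader might infer that unlisted events are lost for the whole four weeks; they are not.
- **Serious events are little affected.** An event meeting the protocol's serious criteria would almost always involve a doctor and so reach 4b or 4c. A reader might infer that serious events go unidentified; the form does not support that.
- **Not every infection lacks a type.** Attended infections have a diagnosis at 4b.
- **Brighton grouping is hardly touched.** Those definitions apply where available, and the ones the protocol sets out are for local reactions and fever, both asked about in Survey 1.
- **The Canterbury form is not clearly defective in the same way.** It is titled as covering medically attended events, its opening question can be read as the stem of the list, and it has no skip to the end. It simply lacks an 'Other' row.
- **The call is described as capturing solicited events.** This is the best defence of the closed list. Against it stand the open wording of item 1 and the undertaking to describe any adverse event. If only listed events were wanted, item 1 would serve no purpose.
- **Layout may have been lost in the text available.** Blank writing space cannot be excluded. The form's other prompts did survive, and none at item 1 asks for a description.

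Rows 4, 6 and 7 of the trace stand after all of this.

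**Conclusion.** The point holds as a limited fault in the Study Two four-week form. An unlisted, unattended event that was not named at the first call is recorded without a term; several such events share one row; and the type of an unattended infection is not recorded. The loss falls mainly on non-serious events and on the description of patterns, not on the overall rate.

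Its size cannot be estimated from the documents. It is tempting to take the 14.6% of adults reporting an unsolicited event after Boostrix, cited in the Canterbury protocol, and compute 0.146 × 300 ≈ 44 women. That figure does not transfer. It comes from adults aged 19–64 under a different solicited list, it includes attended events and events that Survey 1 would name, and the documents give no basis for the share left over.

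The conclusion assumes that the interview follows the printed items and skip, and that item 1 has no description field beyond what the text shows. It is a cheap improvement worth making, not a threat to the study's main safety conclusions.

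**What to change.** - **Study Two, Appendix 7, item 1:** add a free-text line for each event (term, onset, outcome), or an 'Other' row with details, completed for every Yes before the item 4 skip.
- **Study Two, Appendix 7, item 2:** add the infection-type instruction already on the Canterbury form.
- **Canterbury four-week questionnaire:** add an 'Other' row with details for any women still to be surveyed. Its milestones planned last enrolment for December 2012, possibly extended, so this may reach few or none.
- **Data already collected:** report any Yes at item 1 that has no term as unspecified.

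The cost is a form revision, a matching database field, and a few extra minutes of interview for women who answer Yes.

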Appendix 8: Canterbury Protocol

PROTOCOL

Observational study: safety of Tdap administered during pregnancy

Investigator-sponsored study with GSK support

Principle investigator:

[name] FRACP, MD

[figure not shown]
Paediatric Infectious Diseases Specialist

Senior Lecturer, Department of Paediatrics

University of Otago, Christchurch

Background: The Canterbury region is currently experiencing an outbreak of pertussis (whooping cough) with rates of laboratory confirmed disease 10x greater than baseline.¹¹ Most of the infants hospitalised with pertussis infection in the last 5 months have been younger than 6 weeks of age and have therefore not received their first pertussis immunisation.¹¹ Data in New Zealand shows about 20% of infant cases are infected by their mothers.¹²

Canterbury Pertussis Notifications* By Week:
Jan 2011 - 25 May 2012

*Confirmed/Probable

Young infants are generally not protected from pertussis as they are un-immunised and only small amounts of protective antibodies are transferred across the placenta. The main reason

¹¹ Institute for Environmental Science and Research. ESR Pertussis Report; Weeks 14 - 15: 31 Mar - 13 Apr 2012. Wellington: ESR; 2012. Available at http://www.surv.esr.cri.nz/PDF_surveillance/PertussisRpt/2012/201214PertussisRpt.pdf

¹² Walls R. Pertussis (whooping cough) epidemiology in Waikato, New Zealand: 2000-2009. *NZ Med J* 2011;124(1332).

for minimal protection from maternal antibodies is the waning of maternal immunity and low antibody titres in most pregnant women.

Recently the US Advisory Committee on Immunization Practices (ACIP) recommended that acellular pertussis vaccine (Tdap) be given to any person likely to be in contact with young infants under the age of 12 months, including pregnant women.¹³ Administering the vaccine to pregnant women is advised because it not only protects the mother from pertussis but also induces antibodies for the infant at birth which may be protective.³

ACIP acknowledged that the safety of Tdap immunisation during pregnancy has not been systematically studied, with the only data available coming from small studies, postmarketing surveillance, and the the US Vaccine Adverse Event Reporting System (VAERS).¹⁴ They concluded that *“available data from these studies did not suggest any elevated frequency or unusual patterns of adverse events in pregnant women who received Tdap and that the few serious adverse events reported were unlikely to have been caused by the vaccine.”*⁴

The NZ Ministry of Health’s Immunisation Technical Forum (ITF) on vaccines reviewed this recommendation in 2011 and has now recommended the use of Tdap during pregnancy in New Zealand (after 20 weeks).¹⁵ The Ministry of Health also recommends and funds (i.e the vaccine is given at no cost to the woman) influenza vaccination for all pregnant women in NZ.¹⁶

With this in mind, a District Health Board in Canterbury (CDHB) has agreed to fund the administration of Tdap during the current pertussis outbreak to pregnant women (30-36 weeks) and to women in the first 2 weeks after birth.¹⁷

For GPs to be paid for administering the vaccines they need to submit a correctly completed claim form to the CDHB. The usual practice is to submit the claim immediately after the vaccine is given and we would anticipate finding that a claim had been submitted within 1 week of its submission.

Study objectives

Primary Objectives:

- To describe adverse events in women who were administered Tdap between 30-36 weeks of gestation
- To describe outcomes of babies whose mothers were vaccinated with Tdap during week 30 to 36 of pregnancy (including birth history, weight and head circumference and any congenital abnormalities)

Secondary Objectives:

- To describe adverse events in women who were administered the seasonal influenza vaccine during pregnancy
- To describe adverse events in women who were administered the seasonal influenza vaccine and Tdap during pregnancy

¹³ United States Centers for Disease Control and Prevention. Updated recommendations from the Advisory Committee on Immunization Practices (ACIP). *MMWR* 2011; 60(41): 2011

¹⁴ US Advisory Committee on Immunization Practices. Summary Report. Atlanta, Georgia: ACIP; February 23-24, 2011. Available from <http://www.cdc.gov/vaccines/recs/acip/downloads/min-feb11.pdf> Accessed 23 April 2012.

¹⁵ New Zealand Ministry of Health. Current advice on the public health management of pertussis. Wellington: MoH; 5 April 2012. Available at http://www.nzdoctor.co.nz/media/1682109/pertussis_letter_moh_5_apr_2012.pdf

¹⁶ New Zealand Ministry of Health. Chapter 15: Influenza. In Immunisation Handbook 2011. Wellington: MoH; 2011. Available at http://www.google.co.nz/url?sa=t&rct=j&q=ministry%20health%20influenza%20vaccine%20pregnant%20women%20funded%20&source=web&cd=7&ved=0CGYQFjAG&url=http%3A%2F%2Fwww.health.govt.nz%2Fsystem%2Ffiles%2Fdocuments%2Fpublications%2F15influenza.pdf&ei=8SiWT8iDH4_m8Q0gnNGMCg&usg=AFQjCNFUuAYDXQKxJFmtqXKd4PBfzm1i2A

¹⁷ Canterbury District Health Board. Media release from Canterbury DHB: Free whooping cough vaccine extended to pregnant women. Christchurch: CDHB; April 19, 2012.

- To compare adverse event rates in women who were vaccinated with Tdap, seasonal influenza vaccine or both
- To describe outcomes of babies whose mothers were vaccinated with the seasonal influenza during pregnancy (including birth history, weight and head circumference and any congenital abnormalities)
- To describe outcomes of babies whose mothers were vaccinated with the seasonal influenza and also received Tdap during weeks 30-36 of pregnancy (including birth history, weight and head circumference and any congenital abnormalities)
- To Evaluate infants of mothers vaccinated with Tdap, seasonal influenza vaccine or both during pregnancy who have symptoms consistent with pertussis or who have had significant contact with a proven case

Study design

This is a prospective observational cohort study. It will describe any adverse events in pregnant mothers who received either Tdap or influenza vaccine, or both. Outcomes for their infants will also be measured and described. Infants of mothers vaccinated with Tdap, seasonal influenza vaccine or both during pregnancy who have symptoms consistent with pertussis or who have had significant contact with a proven case will also be evaluated. The funded brands of Tdap are Boostrix and Adacel, and the funded brands of influenza are Fluarix and Fluvax).

Study population

Women vaccinated during pregnancy with Tdap will be identified through the GP record of claims for the administration of the vaccine as soon as possible after administration of the vaccine. Women from the same GP practices who have had trivalent inactivated influenza vaccine during pregnancy will also be identified and enrolled..

It is possible women may have received Tdap from sources other than their GP e.g. healthcare workers or women who are seen at hospital with wounds that require a tetanus booster. However it is anticipated this will only be a very small proportion, and the records of claims through the CDHB will accurately reflect the total number of women in Canterbury receiving Tdap during pregnancy.

Identification of women receiving vaccination

Women will be identified as having received vaccination through the claims data submitted to the CDHB. The consent for for Tdap vaccine also asks women if they are happy to be contacted by the study team. Contact details will be obtained from their GP only for women who have indicated they are happy to be contacted.

Informed consent

The Claim form contains basic consent for participation in the study, but an additional consent form (Appendix 1) will be used to obtain signed informed consent for participation and handling of personally identifiable information and safety data.

If a woman chooses not to participate or to withdraw from the study at a later date the reason for non-participation or withdrawal will be recorded.

Confidentiality

Data will be collected and stored on a password protected database located in the Paediatric Department at Christchurch Hospital. The NHI will be used during data collection to identify study participants alongside a study identification number. The study identification number will not include any details that could potentially identify the study participant i.e. date of

birth. The NHI is included because it will provide the easiest access to information from GP records, particularly for newborn infants who may change surnames.

Prior to any data analysis the NHI will be removed from the database and just a study identification number will be used.

Expected sample size

The birth cohort in Canterbury is approximately 6000 per annum. Seasonal influenza vaccines are available in NZ between March and July. Both Tdap and influenza vaccine are funded for pregnant women, but it is very difficult to estimate how many women will take up the vaccines. As of 31st May 2012, 220 claims for the Tdap vaccine had been lodged with the CDHB in 6 weeks. At the 10th June, out of 255 claims processed 22 women had not consented to follow up. There were also a further 53 claims that have been rejected and returned to practices mainly as the consent yes or no was not completed.

Funding for Tdap is being offered postpartum as well as during pregnancy, so women may choose to wait until their babies are born to take up the offer. Funding for the vaccine has approved for an initial period of 6 months with a view to extending for another 6 months if the pertussis outbreak continues. Previous outbreaks in New Zealand have lasted in the order of 18 months so it is likely that funding will continue beyond 6 months. We would therefore aim to enroll 300 women who have received Tdap vaccine.

Study groups

Group 1) received Tdap vaccine while pregnant (30 to 36 weeks gestation).

Group 2) received trivalent inactivated influenza vaccine while pregnant

Group 3) received both Tdap and trivalent inactivated influenza vaccine, separately or coadministered during pregnancy

Inclusion criteria

Women

- Pregnant women 18-40 years of age who have received either the Tdap vaccine between 30-36 weeks gestation, or received the influenza vaccine at any stage during pregnancy or both
- Compliant with routine antenatal care, including at least 1 ultrasound early in pregnancy
- Information regarding which brand vaccine of was given (if the brand is not available, batch number and expiry is sufficient as this will help to ascertain which brand was given)

Infants:

- Infants of the women who were vaccinated with the Tdap vaccine, seasonal influenza vaccine or both during pregnancy

Exclusion criteria

- Pregnant women who have received the Tdap vaccine prior to 30 weeks gestation or after 36 weeks gestation
- If a woman has already had her baby prior to being contacted by the the study team, she will not be enrolled in the study

Statistical Analysis

As this study is an observational study, the pregnancy outcomes and safety data will be descriptive in nature. The rates of AEs and SAEs will be compared to published background rates for the general population (summarised in Tavares et al¹⁰). The expected rates of MAEs and SAEs for Tdap given during pregnancy is unknown, but as a guide the rates of MAEs for pregnant women receiving influenza vaccine in this paper ranged from 1.1 to 3.8% while the rate of SAEs ranged from 0.4 to 1.5%. Where the known background incidence of 0.01 for a particular adverse event, a sample size of 300 achieves 80% power to detect an additional incidence rate of 0.0175 when the significance level is 0.05.

It is anticipated that the difference in AEs between subgroups in the trial will be small. As this is an observational study we therefore plan to describe the confidence intervals for the proportions of AEs within each group. A sample size of 300 produces a two-sided 95% confidence interval with a width equal to 0.081 when the sample proportion is 0.150.

Women who have multiple pregnancies and/or complicated pregnancies will be excluded from the final analyses and described separately.

Related research

In studies of pertussis booster vaccines administered alone or together with influenza vaccine in people 19–64 years of age,¹⁸ adverse reactions were generally mild-to-moderate in intensity. The overall reactogenicity profile of the Tdap and influenza vaccines, in terms of incidence of solicited local symptoms (injection site pain, redness and swelling), as well as the incidence of solicited general symptoms (fatigue, fever, gastrointestinal symptoms, headache, joint pain, muscle aches, and shivering) was generally similar between the co-administration and sequential vaccine groups (Figure).⁸ The most frequently reported local and general solicited symptoms in both vaccine groups were injection site pain and muscle aches, respectively.⁸ Unsolicited adverse events were reported by similar percentages of subjects in both groups (about 20%).⁸

The local symptom report rate was 48.9% after *Fluarix* and 61.6% after *Boostrix*. The rate of unsolicited AE reporting was 17.4% (14.7-20.3) after *Fluarix*, 14.6% (12.1 to 17.3) after *Boostrix*, and 21.5% (18.6-24.6%) after co-administration with both vaccines. The report rate of unsolicited AE causally related to vaccination was 4.3% (2.9 to 6.0) after *Fluarix*, 2.4% after *Boostrix* (1.4-3.8) and 7.0% (5.2-9.0) after co-administration.

The *Boostrix* Data Sheet notes that when Tdap and seasonal influenza vaccine are coadministered in adults, lower levels of antibodies to FHA and pertactin are induced compared to Tdap alone.¹⁹ It is not known if the efficacy of *Boostrix* is affected.⁹

¹⁸ Weston WM et al. Safety and immunogenicity of a tetanus toxoid, reduced diphtheria toxoid, and acellular pertussis vaccine when co-administered with influenza vaccine in adults. *Hum Vaccin*. 2009;5(12):858-66.

¹⁹ GlaxoSmithKline New Zealand. *Boostrix* Data Sheet. GSKNZ; 2011. Available at www.medsafe.govt.nz

¹⁰Tavares et al Pregnancy and safety outcomes in women vaccinated with an AS03-adjuvanted split virion H1N1 (2009) pandemic influenza vaccine during pregnancy: A prospective cohort study. *Vaccine* 2011;29:6358

[figure not shown]

Figure: Percentage of subjects 19–64 years with solicited local and general symptoms during 15 days after vaccination

Fever = oral temperature $\geq 37.5^{\circ}\text{C}$ (99.5°F). Grade 3 referred to redness and swelling of diameter ≥ 50 mm; oral temperature $> 39.0^{\circ}\text{C}$ ($> 102.2^{\circ}\text{F}$); and for all other symptoms, prevented normal activity. From Weston et al, 2009.⁸

Study assessments and procedures

Scheduled assessments	Adverse events in mother	Outcomes for infant	Both mother and baby
At enrolment	
¹First contact with mother by phone (standard script, Appendix 2) as soon as possible after identification to
 
 • Provide information about study and obtain detailed informed consent for participation (written consent form sent out if verbal consent given by phone) • capture any solicited adverse events within first 48 hours and first 7 days of receiving vaccine (s) 
Contact GP once consent obtained to obtain details of vaccination (Appendix 3)
		
Contact with mother monthly either by phone or e-mail⁴. If infant has symptoms* consistent with pertussis or a significant contact** with proven case will be invited for clinical review by study team Paediatrician.
 
If an unsolicited adverse event is noted during these calls, it will follow the same safety reporting procedures as other AEs in the study.

4 weeks since vaccine administration	
²Written questionnaire (Appendix 5) to capture any solicited adverse events in mother up to 4 weeks after receipt of vaccine (s)
		
6-week check	
Written questionnaire (Appendix 6) administered by telephone to GP to
	
Written questionnaire (Appendix 6) administered by telephone to GP practice to
	

Pertussis in Pregnancy Safety (PIPS) Study Protocol
Confidential
Not for Public Circulation or Reproduction

	determine pregnancy outcome and medically attended adverse events in mother since last contact.	capture birth history, weight and head circumference, any congenital abnormalities, neonatal death (<29 days) Details of 6-week check and confirm receipt of 6-week vaccination. Document any prior GP or hospital visits.	
3-6 month check		Weight, head circumference, vaccination status, and standardised clinical examination by Plunket Nurse as recorded in Well Child book (Appendix 6). ³	
1-year follow-up		Final contact with mother about pertussis exposure and/or symptoms. Vaccination status – if not completed infant vaccinations by 6 months.	

¹ Three attempts will be made to contact mother by telephone within 1 week of notification of receipt of Tdap. If an e-mail address is available this will also be used if telephone contact is unsuccessful.

² Written questionnaire will be sent to mother before 4 weeks have elapsed since receipt of vaccine. Telephone contact will be made at 4 weeks of receipt of vaccine and two further times if the completed questionnaire has not been received within 1 week.

³ mothers will be encouraged to attend Plunket for checkups during the first 6 months. If there is no available recorded weight and head circumference between 3-6 months of age this will be done by a member of the the study team. The mother will be contacted 3 times via email or phone to get this information.

⁴ Three attempts will be made by phone or email to contact the mother each month

*Persistent cough lasting for >10 days and/or post-tussive vomiting

** Close contact defined as being in the same room as the person for > 1 hour or 5 minutes of face to face contact with a person with proven pertussis who was symptomatic.

Study instruments

